### **3.6 Schedule of Evaluations**

All subjects who are assigned a SID and receive any investigational product will be followed according to the protocol regardless of the number of doses received, unless consent for follow-up is withdrawn. The investigator must notify the sponsor or designee of deviations from protocol visits or evaluations and, if applicable, these evaluations must be rescheduled or performed at the nearest possible time to the original schedule. Protocol deviations will be recorded on the source document with an explanation for the deviation. The investigator must comply with the applicable requirements related to the reporting of protocol deviations to the Institutional Review Board (IRB)/ Independent Ethics Committee (IEC).

Subjects/legal representatives will be instructed to call study personnel to report any abnormalities during the intervals between study visits and to come to the study site if medical evaluation is needed and the urgency of the situation permits. For emergency and other unscheduled visits to a medical facility other than the study site, medical records will be obtained by the investigator and made available to the sponsor or designee during monitoring visits.

A schedule of screening and on-study visit procedures is presented in [Table 3.6-1](#) and [Table 3.6-2](#), and a schedule of follow-up visit procedures is presented in [Table 3.6-3](#), followed by a detailed description of each visit. All visits during Cycle 2 and subsequent visits may occur in a  $\pm$  2-day window to accommodate schedule changes, but doses of MEDI-575 must not occur more frequently than every 6 days if in the weekly schedule or every 19 days if in the every 3-week schedule.

For Cohorts 6 and 7, and subjects enrolled in the every 3-week schedule of the dose-expansion phase, visits and study procedures on Study Days 8 and 15 are required only

during the first cycle. For Cycle 2 and subsequent cycles, no Study Day 8 or Study Day 15 visits are required.

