### **Treatment:**

In the dose-escalation phase (through Cohort 5), subjects will be treated with 1 of 5 doses of MEDI-575 (3.0, 6.0, 9.0, 12, or 15 mg/kg) once every 7 days (Table 3.5.2-1). Subjects enrolled in Dose Cohort 1 (3.0 mg/kg) only will receive as a 60-minute IV infusion a single lead-in dose of MEDI-575 at 0.5 mg/kg administered 7 days prior to receipt of the first dose of MEDI-575 at the 3.0 mg/kg dose level. The single lead-in dose at 0.5 mg/kg will be used

to assess PK and pharmacodynamic parameters. The day of administration of the 0.5 mg/kg dose will be considered the day of initiation of treatment (Study Day 1). The DLT period for this dose cohort only will begin with the single administration of MEDI-575 at the dose level of 0.5 mg/kg and continue until 21 days after administration of the first dose at 3.0 mg/kg (Study Day 28) for a total of 28 days. Thereafter MEDI-575 will be administered as a 60-minute IV infusion on Study Days 1, 8, and 15 of each 21-day treatment cycle until unacceptable toxicity, documentation of disease progression, or other reasons for subject withdrawal (see Section 4.7). In Cycle 2 and beyond, a dose can be delayed up to 7 days based on hematologic and nonhematologic toxicities, according to the conditions described in Section 3.5.5 (Dose Modifications and Toxicity Management), but all 3 planned doses (if a subject is enrolled on the weekly dosing schedule) must be completed within the cycle. Subjects enrolled on the weekly dosing schedule who do not receive all 3 doses within a cycle will not advance to the next cycle and will be removed from treatment; therefore, each cycle after the first cycle of the weekly dosing schedule will be considered complete after administration of 3 doses. For the weekly dosing schedule, each new cycle will begin no fewer than 7 days after the last dose of the previous cycle; and for the every 3-week dosing schedule, each new cycle will begin no fewer than 21 days after the last dose of the previous cycle. Rules for dose escalation are described in Section 4.9. Intrasubject dose escalation, except for the first cohort as described above, will not be allowed. Dose reduction for toxicities other than DLTs (see Section 4.10 for definition of DLTs) will be allowed as described in Section 3.5.5.

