Two additional cohorts will be added to the dose-escalation phase to evaluate 25 mg/kg (Dose Cohort 6) and 35 mg/kg (Dose Cohort 7) administered as a 90-minute IV infusion once every 21 days on Study Day 1 of each cycle. The infusion time is increased for the 25 or 35 mg/kg doses (every 3-week schedule) due to the larger protein load. These subjects will be evaluated identically to other subjects during dose escalation, since the cycle length and DLT period will be 21 days. Subjects in Cohorts 6 and 7 will be considered evaluable if they receive a single dose of MEDI-575 and complete the 21-day DLT period or discontinue due to DLTs. The doses and schedule were chosen based on PK and pharmacodynamic modeling and data obtained in the first 3 treated cohorts, and are predicted to provide target saturation of PDGFR $\alpha$  receptors for the duration of the dosing interval. A minimum of 21 evaluable subjects or up to approximately 42 evaluable subjects will be required during the dose-escalation phase.

Pharmacokinetic/pharmacodynamic modeling was performed based on data generated in cynomolgus monkey PK studies and the first 2 cohorts (3 and 6 mg/kg) from this protocol. The PK/pharmacodynamic model accurately predicted the serum concentrations obtained in humans following the 3, 6, and 9 mg/kg dose of MEDI-575 in this study. Based on the PK/pharmacodynamic modeling, preclinical xenograft efficacy data, and the human data obtained to date, including the measurement of PDGF-AA in the serum, a predicted target average concentration of 250  $\mu$ g/mL and trough levels above 150  $\mu$ g/mL were identified. These concentrations ensure consistent saturation of PDGFR $\alpha$  receptor over the entire dosing interval and are predicted to provide maximum antitumor activity based on animal models. This effect is predicted to be achieved with a dosing schedule of 25 mg/kg or greater administered every 3 weeks. In the current study, no DLTs have been observed in the first 5 cohorts. The increase in dosing interval is under investigation in order to evaluate the feasibility of administration in conjunction with standard chemotherapeutic regimens. This dose regimen will be compared to the once-weekly dosing regimen in the dose-expansion

phase. The prolonged schedule should still allow for adequate blood concentrations as described above to achieve potential antitumor effects.

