#### 3.5.2 Treatment Regimen

In the weekly schedule of the dose-escalation phase (Cohorts 1 through 5), subjects will be treated with 1 of 5 doses of MEDI-575 (3.0, 6.0, 9.0, 12, or 15 mg/kg) once every 7 days (Table 3.5.2-1). Subjects enrolled in Dose Cohort 1 (3.0 mg/kg) only will receive as a

60-minute IV infusion a single lead-in dose of MEDI-575 at 0.5 mg/kg administered 7 days prior to receipt of the first dose of MEDI-575 at the 3.0 mg/kg dose level. The single lead-in dose at 0.5 mg/kg will be used to assess PK and pharmacodynamic parameters. The day of administration of the 0.5 mg/kg dose will be considered the day of initiation of treatment (Study Day 1). The DLT period for this dose cohort only will begin with the single administration of MEDI-575 at the dose level of 0.5 mg/kg and continue until 21 days after administration of the first dose at 3.0 mg/kg (Study Day 28) for a total of 28 days. Thereafter MEDI-575 will be administered as a 60-minute IV infusion on Study Days 1, 8, and 15 of each 21-day treatment cycle until unacceptable toxicity, documentation of disease progression, or other reasons for subject withdrawal (see Section 4.7). In Cycle 2 and beyond, a dose can be delayed up to 7 days based on hematologic and nonhematologic toxicities, according to the conditions described in Section 3.5.5 (Dose Modifications and Toxicity Management), but all 3 planned doses (if a subject is enrolled in the weekly dosing schedule) must be completed within the cycle. Subjects enrolled in the weekly dosing schedule who do not receive all 3 doses within a cycle will not advance to the next cycle and will be removed from treatment; therefore, each cycle after the first cycle of the weekly dosing schedule will be considered complete after administration of 3 doses. For the weekly dosing schedule, each new cycle will begin no fewer than 7 days after the last dose of the previous cycle. For the every 3-week schedule (Dose Cohorts 6 and 7, 25 mg/kg and 35 mg/kg, respectively) of the dose-escalation phase, MEDI-575 will be administered as a 90-minute IV infusion once every 21 days (on Study Day 1 of a 21-day cycle). Each new cycle will begin no fewer than 21 days after the last dose of the previous cycle. Rules for dose escalation are described in Section 4.9. Intrasubject dose escalation, except for the first cohort as described above, will not be allowed. Dose reduction for toxicities other than DLTs (see Section 4.10 for definition of DLTs) will be allowed as described in Section 3.5.5.

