#### **3.5.5 Dose Modifications and Toxicity Management**

Dose modifications of MEDI-575 will be based on hematologic and nonhematologic toxicities that cannot be attributed to another cause, such as disease progression or accident, following the first cycle of treatment ([Table 3.5.5-1](#)). Both hematologic and nonhematologic

toxicities will be graded according to NCI CTCAE V3.0. All DLTs must be documented as an AE on the source document. If enrolled in the weekly schedule, a cycle will be considered complete after administration of 3 doses for all cycles after the first cycle. If enrolled in the every 3-week schedule, a cycle will be considered complete after the administration of 1 dose.

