#### **4.9 Dose Escalation**

Rules for dose escalation are as follows:

- 1) Subjects enrolled in Dose Cohort 1 (3.0 mg/kg) only will receive a single, lead-in dose of MEDI-575 at 0.5 mg/kg administered 7 days prior to receipt of the first dose of MEDI-575 at the 3.0 mg/kg dose level. The DLT period for this dose cohort only will begin with the single administration of MEDI-575 at the dose level of 0.5 mg/kg (Study Day 1) and continue until 21 days after the administration of the first dose of MEDI-575 at the 3.0 mg/kg dose level (Study Day 28). Any DLTs that occur in subjects in this cohort after the administration of the lead-in dose, but prior to

administration of the first dose at the 3.0 mg/kg dose level will be considered related to the 0.5 mg/kg dose. DLTs that occur after MEDI-575 has been administered at a dose of 3.0 mg/kg will be considered related to the 3.0 mg/kg dose. Dose escalation and administration of investigational product for this and all subsequent cohorts will follow the rules outlined below.

- 2) Dose escalation will begin with a single subject in each dose cohort. If no DLTs (as defined in Section 4.10) are observed in this subject within the first 7 days of administration of MEDI-575, 2 additional subjects will be enrolled into that dose cohort and may be dosed immediately.
- 3) If no DLTs are observed in the first 3 subjects treated in the dose cohort through the first 28 days (Dose Cohort 1) or 21 days (Dose Cohort 2 and above) of administration of MEDI-575, enrollment into the next higher dose cohort will begin using the same rules described in Item 2.
- 4) If 1 out of 3 subjects within a dose cohort experiences a DLT, that dose cohort will be expanded to a total of 6 subjects provided no further subjects experience a DLT. If no further subjects experience a DLT through the first 28 days (Dose Cohort 1) or 21 days (Dose Cohort 2 and above) of administration of MEDI-575 in the expanded dose cohort, dose escalation will continue in the next higher dose cohort using the same rules described in Item 2.

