- 5) If 2 or more subjects within a dose cohort experience a DLT within the first 28 days (Dose Cohort 1) or 21 days (Dose Cohort 2 and above) of administration of MEDI-575, then the MTD will be exceeded and no further subjects will be enrolled into that dose cohort. If this happens, the preceding dose cohort will be evaluated as the MTD, with the addition of 3 subjects if this dose cohort has not previously been expanded to 6 subjects. If  $\leq 1$  of 6 subjects experiences a DLT, this dose will be declared the MTD. Approximately 6 additional subjects will be enrolled into the MTD dose cohort as well as the dose cohort below the MTD dose cohort to evaluate PK and pharmacodynamic parameters and determine tumor response.
- 6) If the MTD is not reached at a dose of 15 mg/kg/week, a dose will be determined from Cohorts 1 through 5 using a combination of PK, pharmacodynamic markers, safety, and when available, efficacy data. The maximum dose for the weekly schedule will be 15 mg/kg. This weekly dose level will be used in the dose-expansion phase as the weekly dose-expansion dose. Two additional cohorts will also be added at 25 mg/kg (Dose Cohort 6) and 35 mg/kg (Dose Cohort 7) administered as a 90-minute IV infusion once every 21 days (on Study Day 1) to the dose-escalation phase. One of these doses (based on PK, pharmacodynamic markers, safety, and, when available, efficacy data) will be used in the dose-expansion phase as the every 3-week expansion dose. The subjects enrolled in Cohorts 6 and 7 will be evaluated identically to subjects in Cohorts 1 through 5 in the dose-escalation phase. The decision to escalate from 25 mg/kg to 35 mg/kg will be made using the same parameters as those used for the weekly dosing schedule.

- 7) The dose-expansion phase will consist of approximately 12 subjects. Approximately 6 subjects will be treated once every 7 days of a 21-day cycle (weekly schedule) at a dose identified by the criteria in Item 6 from Cohorts 1 through 5. Another 6 subjects will be treated once every 21 days on Study Day 1 (every 3-week schedule) at a dose identified by the criteria in Item 6 from Cohorts 6 and 7. The subjects in these dose-expansion cohorts must have one of the following advanced solid tumors: NSCLC, GBM, ovarian cancer, or synovial sarcoma.

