#### **4.10 Definitions of Dose-limiting Toxicities**

Dose-limiting toxicities will be graded according to the NCI CTCAE V3.0. The DLT period for Dose Cohort 1 only will begin with the single lead-in administration of MEDI-575 at the dose level of 0.5 mg/kg (Cycle 1, Study Day 1) and continue through the entire first cycle of treatment (Cycle 1, Study Day 28) for a total of 28 days. The DLT period for Dose Cohorts 2

through 7 will begin with the administration of the first dose of MEDI-575 and continue through the entire first cycle of treatment (Cycle 1, Study Day 1 through Cycle 1, Study Day 21).

A DLT is defined as:

- 1) Any Grade 3 or higher non-hematologic toxicity that occurs during the DLT assessment period where a cause other than the investigational product (such as disease progression or accident) cannot be reasonably justified with the following exceptions:
  - Grade 3 fever (in the absence of neutropenia) defined as  $> 40.0^{\circ}\text{C}$  ( $>104.0^{\circ}\text{F}$ ) that resolves to normal or baseline within 24 hours of treatment and is not considered an SAE; or
  - Grade 3 rigors/chills that respond to optimal therapy.
- 2) Any Grade 3 or higher hematologic toxicity where a cause other than the investigational product (such as disease progression or accident) cannot be reasonably justified.

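### Section 3.6 allows every-3-week doses 19 days apart, against the 21-day minimum in Section 3.5.2, so a second dose can fall inside the single-dose DLT period of Cohorts 6 and 7

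*Protocol*

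**What the plan says.** Two parts of the protocol set a minimum gap between every-3-week doses.

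- **Section 3.6 (Schedule of Evaluations)** allows visits from Cycle 2 onward to move by 2 days either way, provided doses "must not occur more frequently than every 6 days if in the weekly schedule or every 19 days if in the every 3-week schedule". Cycle 2 Day 1 is not exempted.
- **Section 3.5.2 (Treatment Regimen)**, for Cohorts 6 and 7: "Each new cycle will begin no fewer than 21 days after the last dose of the previous cycle". The Treatment part of the Study Abstract says the same: "for the every 3-week dosing schedule, each new cycle will begin no fewer than 21 days after the last dose of the previous cycle".

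Three further provisions fix what the gap means.

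- **Section 3.5.5**: "If enrolled in the every 3-week schedule, a cycle will be considered complete after the administration of 1 dose".
- **Section 2.4**: "Subjects in Cohorts 6 and 7 will be considered evaluable if they receive a single dose of MEDI-575 and complete the 21-day DLT period", or stop because of a DLT.
- **Section 4.10** has the DLT period for Cohorts 2 to 7 start at the first dose and "continue through the entire first cycle of treatment (Cycle 1, Study Day 1 through Cycle 1, Study Day 21").

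Section 4.9 counts DLTs by elapsed days: "through the first 28 days (Dose Cohort 1) or 21 days (Dose Cohort 2 and above) of administration of MEDI-575". It carries the same rules over to the every-3-week cohorts: "The decision to escalate from 25 mg/kg to 35 mg/kg will be made using the same parameters".

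**The concern.** On the every-3-week schedule each cycle holds one dose, so every interval between doses is also a boundary between cycles. The 19-day and 21-day minimums therefore apply to the same interval. Neither section refers to the other or says which prevails. A dose given after 19 or 20 days complies with Section 3.6 and deviates from Section 3.5.2.

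The place where this matters is Cycle 2 Day 1 in Cohorts 6 and 7. Their DLT period is built around one dose and 21 days of observation. A second dose on Day 20 or 21 falls inside it.

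A Grade 3 or higher event on those days with no other reasonable cause would then meet two rules. Under the day count in Section 4.9 it is most naturally a DLT of the first dose, although it may follow the second. Under Section 3.5.5 it is also a second-cycle toxicity, which suspends escalation for review if it is at least possibly attributable to the product.

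Sites that follow different sections would also observe subjects of one 3+3 cohort under different exposure. With 3 to 6 subjects per cohort, the classification of one event can decide the step from 25 to 35 mg/kg, and finding the MTD is a primary objective.

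**Working it through.** **Inputs.** First dose on Study Day 1. Nominal interval 21 days (Table 3.5.2-1). Window ±2 days and floor 19 days (Section 3.6). Minimum 21 days (Section 3.5.2). DLT period Day 1 to Day 21 (Section 4.10).

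**Where the 19 comes from.** 21 − 2 = 19, so the floor in Section 3.6 is the nominal interval less the window. Nominal Cycle 2 Day 1 is 1 + 21 = Day 22, and its earliest date under the window is 22 − 2 = Day 20.

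**Each possible gap, every-3-week schedule:**

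| Gap (days) | Study Day of dose 2 | Section 3.6 | Section 3.5.2 | DLT-period days on or after dose 2 |
|---|---|---|---|---|
| 19 | 20 | allowed | barred | 2 of 21 (9.5%) |
| 20 | 21 | allowed | barred | 1 of 21 (4.8%) |
| 21 | 22 | allowed | allowed | 0 |

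**Weekly schedule for comparison.** The last Cycle 1 dose in Cohorts 2 to 5 is on Day 15. Six days later is Day 21, inside the DLT period; seven days later is Day 22, outside it. Here the two sections can be reconciled, with 6 days as the floor within a cycle and 7 days at the boundary, but Section 3.6 does not say so. The every-3-week schedule has no within-cycle interval, so this reading is not available there.

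**Subjects affected.** Two cohorts of 3 to 6: 2 × 3 = 6 to 2 × 6 = 12 evaluable subjects.

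**Possible effect on escalation.** A cohort escalates with 0 DLTs in 3 subjects, or with 1 in the first 3 and 0 in the next 3. With per-subject DLT probability p:

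E(p) = (1 − p)³ + 3p(1 − p)² × (1 − p)³

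For p = 0.10: 0.729 + 0.3 × 0.81 × 0.729 = 0.729 + 0.177 = 0.906.

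The protocol gives no event rate. The base rates and the points added by a second dose in every subject are assumptions:

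| Base p | E(p) | Fall, +1 point | Fall, +2 points | Fall, +5 points |
|---|---|---|---|---|
| 0.05 | 0.973 | 0.011 | 0.023 | 0.067 |
| 0.10 | 0.906 | 0.017 | 0.035 | 0.092 |
| 0.20 | 0.709 | 0.022 | 0.044 | 0.109 |

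At base 0.10 the resulting values are 0.889, 0.871 and 0.814. As a guide to the likely addition, risk spread evenly over the period gives 0.10 × 2/21 = 0.0095, about 1 point. A larger addition would need risk concentrated on the day of infusion or soon after it.

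**The case against.** The strongest reply is that both rules can be obeyed. The dose clause in Section 3.6 is a prohibition and does not entitle a site to dose at 19 days. A site that always waits 21 days breaches nothing. This is true, but it leaves Section 3.6 with a floor that can never be reached, and a site reading that section alone would take a 19-day gap as permitted.

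A second reply is that cycles are fixed at 21 days, so a Day 20 or 21 visit is not clearly a Cycle 2 visit and the window may not reach it. The text does allow that reading. However, Cycle 2 Day 1 is a Cycle 2 visit in Table 3.6-2, and the 19-day figure has a use only if that visit can come early.

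Third, a late event would be looked at individually. Section 4.9 requires a joint safety review before escalation, Section 4.6 adds the Safety Monitoring Committee, and counting the event as a DLT would err toward slower escalation. This limits the harm. It does not settle which dose or which rule the event belongs to.

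It is also fair that the single dose in Section 2.4 is an evaluability condition, and no text makes a subject non-evaluable because of a later dose. The larger falls in escalation probability rest on a 5-point addition and early dosing in every subject, and should be read as an outer range.

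**Conclusion.** The inconsistency is real. Section 3.6 is wrong as written for the every-3-week schedule, and this conclusion does not depend on any assumed event rate. If the early side of the window is used at Cycle 2 Day 1, a second dose falls on Day 20 or 21, and the DLT period of that subject no longer reflects one dose throughout.

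The practical size is small. At most 2 of 21 days are affected, in 6 to 12 subjects. With an even spread of risk and a 10% base rate, the loss in escalation probability is about 0.017, and the assumed range runs from 0.011 to 0.109. It is zero if no site doses early. Section 1.4 reports that Cohorts 1 to 5 have enrolled with no DLTs so far, and the expansion phase carries no 3+3 decision. This is a correction worth making, and it does not threaten the design.

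**What to change.** In Section 3.6, replace the 19-day floor with 21 days for the every-3-week schedule, and set the window on Day 1 of each cycle to 0 to +2 days. Cycle 2 Day 1 at the nominal spacing then falls on Day 22 to 24, after the DLT period. State as well that the 6-day weekly floor applies only within a cycle, with 7 days at the cycle boundary. No Cycle 2 dose in Cohorts 2 to 7 is then given before Day 22.

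If the sponsor wants 19 days for later cycles, amend Section 3.5.2 and the matching sentence of the Study Abstract to allow it from Cycle 3 onward, and bar the minus side of the window at Cycle 2 Day 1.

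The first option changes one sentence and the second two more. Either needs sponsor approval, regulatory submission and IRB/IEC approval under Section 10, so it is best bundled with another amendment if one is due before Cohort 6 opens. The operational cost of the first option is that Day 1 of a cycle cannot be brought forward, and a delay carries into later cycles. Section 3.5.2 already imposes both on the every-3-week schedule.
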